6.3 Other Grade 3 or 4 Non-Hematologic Toxicity

Adverse events associated with anti-estrogen therapy will vary by medication. The treating investigator should consult the currently approved package insert and watch for signs and symptoms of expected and possible AEs. There are no dose reduction sections for these therapies. If Grade 3 (or chronic Grade 2) toxicity attributed to anti-estrogen therapy occurs, the drug may be stopped for up to 2 weeks and then restarted. Patients may continue everolimus treatment if anti-estrogen therapy is held. If toxicity does not improve or resolve with a treatment break, or recurs and is intolerable to the patient, the anti-estrogen therapy should be discontinued.

7. STUDY ASSESSMENTS AND EVALUATIONS

7.1 Overview

All patients must visit the study center on the days specified within this protocol. The complete Schedule of Assessments for this study is shown in Appendix D. The baseline physical examination, medical history, ECOG PS, complete blood counts (CBCs), comprehensive metabolic profile (CMP), serum pregnancy test for pre/peri menopausal women (regardless of ovarian suppression), and urinalysis must be done \leq 7 days prior to initiation of treatment. However, if these initial examinations are obtained within 72 hours of Cycle 1 Day 1 they do not have to be repeated. CT Scans and MRIs to document measureable disease must be performed \leq 4 weeks prior to initiation of treatment.

CONFIDENTIAL

STUDY DRUG(S): EVEROLIMUS
FINAL PROTOCOL DATE: 19 JUNE 2014

SCRI INNOVATIONS STUDY NUMBER: BRE 212
VERSION 1.0

Review medical history to determine if patient requires hepatitis B and/or hepatitis C testing. Hepatitis serology (See Appendix D) will be required at screening if the patient is in the following risk categories:

- Currently lives in (or has lived in) Asia, Africa, Central and South America, Eastern Europe, Spain, Portugal, or Greece.
- Has any of the following risk factors:
 - known or suspected past hepatitis B infection,
 - known or suspected past hepatitis C infection (including past interferon ‘curative’ treatment)
 - blood transfusion(s) prior to 1990,
 - current or prior IV drug use,
 - current or prior dialysis,
 - household contact with hepatitis B or hepatitis C infected person(s)
 - current or prior high-risk sexual activity,
 - body piercing or tattoos,
 - biological mother known to have hepatitis B infection
 - history suggestive of hepatitis B infection (e.g., dark urine, jaundice, right upper quadrant pain) or
 - any other risk factors as determined

Positive hepatitis serology at screening will make the patient ineligible for this study.

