8. Impairment of gastrointestinal function or gastrointestinal (GI) disease that may significantly alter absorption of everolimus (e.g., ulcerative disease, uncontrolled nausea, vomiting, diarrhea, malabsorption syndrome, or small bowel resection).
9. Patients with known active hepatitis B (HBV) or hepatitis C (HCV) infection. Patients with risk factors for hepatitis (See Section 7.1) must have HBV DNA and HCV RNA testing by PCR, and are ineligible if these tests are positive.
10. Concurrent use of strong CYP3A4 inhibitors or inducers from 72 hours prior to initiation of study treatment until the end of treatment with everolimus (See Section 5.5).
11. Chronic treatment with systemic steroids or other immunosuppressive agents. Note: Topical or inhaled corticosteroids are allowed.
12. Patients receiving immunization with attenuated live vaccines within 1 week of study entry or during study period (See Section 5.4).

CONFIDENTIAL

STUDY DRUG(S): EVEROLIMUS
FINAL PROTOCOL DATE: 19 JUNE 2014

SCRI INNOVATIONS STUDY NUMBER: BRE 212
VERSION 1.0

13. Pregnant or lactating women or women of childbearing potential without a negative serum pregnancy test, ≤ 7 days prior to date of first treatment, regardless of the method of contraception used.
14. Patients with known human immunodeficiency virus (HIV) seropositivity.
15. History of other malignancy ≤ 5 years of study entry which could affect compliance with the protocol or interpretation of results. Note: History of curatively treated basal or squamous cell carcinoma of the skin or in situ carcinoma of the cervix, or ductal carcinoma in situ (DCIS) of the breast treated with lumpectomy alone with curative intent, are generally eligible.
16. Significant concurrent, uncontrolled medical condition which, in the opinion of the investigator, may interfere with patient participation in the study.

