6.2.10 Management of Hepatitis Reactivation/Flare

Reactivation of hepatitis B (HBV) has been observed in patients with cancer receiving chemotherapy (Yeo W. et al. 2004). Sporadic cases of hepatitis B reactivation have also been seen in this setting with everolimus. In cancer patients with hepatitis B, whether carriers or in chronic state, use of antivirals during anti-cancer therapy has been shown to reduce the risk of hepatitis B virus reactivation and associated morbidity and mortality (Loomba R. et al. 2008). A detailed assessment of hepatitis B or C medical history and risk factors must be done for all patients at screening, with testing performed prior to the first dose of everolimus.

Patients with known hepatitis, or positive hepatitis serology, are ineligible to enroll in this study.

CONFIDENTIAL

STUDY DRUG(S): EVEROLIMUS
FINAL PROTOCOL DATE: 19 JUNE 2014

SCRI INNOVATIONS STUDY NUMBER: BRE 212
VERSION 1.0

Patients found to have positive hepatitis serology while on study may continue treatment but must receive appropriate hepatitis prophylaxis during the remainder of their treatment with everolimus and for 4 weeks after everolimus is discontinued.

Monitoring and prophylactic treatment for Hepatitis B reactivation

Table 6 provides details of monitoring and prophylactic therapy according to the baseline results of viral load and serologic markers testing.

Table 6 Action Required for Positive Hepatitis B Results While Receiving Everolimus

Test	Result	Result	Result	Result	Result
HBV-DNA	+	+ or -	-	-	-
HBsAg	+ or -	+	-	-	-
HBsAb	+ or -	+ or -	+	+ or -	-
HBcAb	+ or -	+ or -	+ or -	+	-
Recommendation	Prophylaxis treatment should be started 1-2 weeks prior to first dose of everolimus Monitor HBV-DNA every 4 - 8 weeks.		No prophylaxis treatment. Monitor HBV-DNA every 3-4 weeks.		No specific action.

Antiviral prophylaxis therapy should continue for at least 4 weeks after last dose of everolimus. Hepatitis B reactivation definition and management guidelines are defined below in Table 7.

CONFIDENTIAL

STUDY DRUG(S): EVEROLIMUS
FINAL PROTOCOL DATE: 19 JUNE 2014

SCRI INNOVATIONS STUDY NUMBER: BRE 212
VERSION 1.0

Table 7 Guidelines for Management of Hepatitis B

HBV reactivation (with or without clinical signs and symptoms)*	
Baseline Results	Actions

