Positive HBV-DNA OR Positive HBsAg Reactivation is defined as: Increase of 1 log in HBV-DNA relative to baseline HBV-DNA value OR New appearance of measurable HBV-DNA	Start a second antiviral medication AND Interrupt everolimus administration until resolution: 
 ≤ baseline HBV-DNA levels If resolution occurs within ≤ 28 days , everolimus should be re-started at one dose lower, if available. (See Table 1 for dose levels available) If the patient is already receiving the lowest dose of everolimus according to the protocol, the patient should restart at the same dose after resolution. Both antiviral therapies should continue at least 4 weeks after last dose of everolimus. If resolution occurs > 28 days , Patients should discontinue everolimus but continue both antiviral therapies at least 4 weeks after last dose of everolimus.
Negative HBV-DNA and HBsAg AND Positive HBsAb (with no prior history of vaccination against HBV), OR Positive HBcAb Reactivation is defined as: New appearance of measurable HBV-DNA	Start first antiviral medication AND Interrupt everolimus administration until resolution: 
 ≤ undetectable (negative) HBV-DNA levels If resolution occurs within ≤ 28 days , everolimus should be re-started at one dose lower, if available (See Table 1 for dose levels available). If the patient is already receiving the lowest dose of everolimus according to the protocol, the patient should restart at the same dose after resolution. Antiviral therapy should continue at least 4 weeks after last dose of everolimus. If resolution occurs > 28 days , discontinue everolimus but continue antiviral therapy at least 4 weeks after last dose of everolimus.

* All reactivations of HBV are to be recorded as Grade 3 (e.g. CTCAE Version 4.0 - Investigations/Other: Viral Reactivation) (<http://evs.nci.nih.gov/ftp1/CTCAE/CTCAE>), unless considered life threatening by the investigator, in which case they should be recorded as Grade 4. Date of viral reactivation is the date on which the rise or reappearance of HBV-DNA was recorded.

Monitoring and Management of Hepatitis C

Two groups of patients will require monitoring every 4 -8 weeks for HCV flare during this study:

- Patients with detectable HCV RNA-PCR test at baseline.
- Patients known to have a history of HCV infection, despite a negative viral load test at baseline (including those that were treated and considered “cured”).

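### Hepatitis eligibility and management text conflict: exclusion 9 does not name serology, Sections 7.1 and 6.2.10 exclude on it, Tables 6–8 provide for baseline-positive patients, and Appendix D omits the viral monitoring

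*Protocol*

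**What the plan says.** **Eligibility.** Exclusion criterion 9, in the synopsis and in protocol Section 3.2, bars "Patients with known active hepatitis B (HBV) or hepatitis C (HCV) infection". It adds that patients with risk factors "must have HBV DNA and HCV RNA testing by PCR, and are ineligible if these tests are positive". Section 7.1 lists the risk factors that trigger testing and ends: "Positive hepatitis serology at screening will make the patient ineligible for this study". Section 6.2.10 says: "Patients with known hepatitis, or positive hepatitis serology, are ineligible to enroll in this study".

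**Tests.** Section 7.2 gives the screening panel for at-risk patients: HBV DNA, surface antigen (HBsAg), core antibody (HBcAb), surface antibody (HBsAb), and HCV RNA. No HCV antibody test is listed. Section 7.1 refers to Appendix D for hepatitis serology, and note o there lists the same five tests.

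**Management.** Section 6.2.10 introduces Table 6 as giving monitoring and prophylaxis "according to the baseline results of viral load and serologic markers testing". For patients positive for HBV DNA or HBsAg, Table 6 says "Prophylaxis treatment should be started 1-2 weeks prior to first dose of everolimus". For patients negative on both but positive for HBsAb or HBcAb, it gives no prophylaxis and HBV DNA monitoring every 3–4 weeks. Table 7 defines HBV reactivation by baseline group. The groups to be monitored for HCV flare every 4–8 weeks include "Patients with detectable HCV RNA-PCR test at baseline", and Table 8 has a row for them. A separate sentence in 6.2.10 says "Patients found to have positive hepatitis serology while on study may continue treatment", with prophylaxis.

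**Schedule.** Section 7.1 describes Appendix D as the complete schedule. Its hepatitis row is marked at baseline only.

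**The concern.** An eligibility rule has to give one answer for one set of test results. Here the formal exclusion list and the assessment section give different answers for an identifiable group, and the management tables are written as if patients barred by one or both had been enrolled. Sites could then admit different patients under the same protocol.

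The safety side is the monitoring. Section 6.2.1 names hepatitis B reactivation among the infections seen with everolimus and says of these infections as a group that some were severe and occasionally fatal. Section 6.2.10 describes reactivation with everolimus as sporadic. A site that works from the visit schedule would not find the tests meant to detect it. No data monitoring committee is used (Section 10.6), so the site-level rules matter.

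**Working it through.** No arithmetic applies. The check sets each baseline result against each passage.

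| Baseline result | Exclusion 9 | Sections 7.1 and 6.2.10 | Tables 6–8 and HCV list |
|---|---|---|---|
| HBV DNA and HBsAg negative, HBcAb positive | PCR test does not exclude | Excluded | No prophylaxis, HBV DNA every 3–4 weeks (Table 6); reactivation rule (Table 7) |
| HBV DNA, HBsAg and HBcAb negative, HBsAb positive from vaccination | PCR test does not exclude | Excluded on a literal reading | Monitored under Table 6; outside the Table 7 group |
| HBV DNA negative, HBsAg positive | PCR test does not exclude; excluded if judged known active infection | Excluded | Prophylaxis before first dose, HBV DNA every 4–8 weeks (Table 6) |
| HBV DNA positive | Excluded | Excluded if serology means the note o tests | Prophylaxis before first dose (Table 6) |
| HCV RNA positive | Excluded | Excluded if serology means the note o tests | Monitored every 4–8 weeks; flare rule (Table 8) |
| Past HCV, RNA negative | PCR test does not exclude | 7.1: past infection triggers testing; 6.2.10: excluded if past infection counts as known hepatitis | Monitored every 4–8 weeks; flare rule (Table 8) |

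Four things follow.

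1. **Who may enrol.** The first three rows are the sharpest conflict: PCR-negative patients with a positive hepatitis B marker. Criterion 9 names no marker that excludes them (unless an HBsAg-positive patient is judged to have known active infection), while 7.1 and 6.2.10 do exclude them. Table 7 sets aside surface antibody in patients with a vaccination history; 7.1 and Table 6 carry no such qualifier.

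2. **HCV is narrower.** The only HCV screening test is RNA, so 7.1 adds no antibody criterion to criterion 9. What remains is the management text for RNA-positive patients, and the difference between known hepatitis (6.2.10) and known active infection (criterion 9).

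3. **Management against eligibility.** HBV DNA-positive and HCV RNA-positive patients are excluded by criterion 9 itself, yet Tables 6–8 and the HCV list tell sites how to handle them from baseline. For these patients the eligibility text agrees that they are out, and the conflict is with the management text.

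4. **Schedule.** The intervals of 3–4 and 4–8 weeks stand in 6.2.10. Appendix D has no matching entry after baseline, and the visit lists in Sections 7.3.1 to 7.3.3 and 7.5 contain no viral test.

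**The case against.** The strongest reply is that exclusions accumulate. Criterion 9 does not say that PCR is the sole test, it points to Section 7.1, and 6.2.10 repeats the serology exclusion. A careful site would exclude on either result, and the likelier enrolment error is excluding too many. This has force: a reader might infer that criterion 9 admits everyone who is PCR negative, and it does not say so. But its pointer to 7.1 is attached to the risk factors, serology is missing from the formal exclusion list, and under the combined reading most of Tables 6–8 would describe patients who cannot be on study.

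A second reply is that Table 6 covers positivity found during treatment, as its title suggests. The sentence allowing patients found positive on study to continue is indeed not a contradiction by itself. But the introduction ties Table 6 to baseline results, and an action set before the first dose cannot apply to someone already treated. The on-study reading also adds a conflict: 6.2.10 requires prophylaxis for patients found serology-positive on study, while Table 6 gives none to those positive only for antibody.

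A reader might also infer a third stated rule, that baseline-positive patients are eligible if given prophylaxis. No passage says this; it is only implied by the management tables. Nor is monitoring absent from the protocol: the intervals are given, and what is missing is their entry in Appendix D.

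**Conclusion.** The inconsistency is real and has three parts: serology is grounds for exclusion in 7.1 and 6.2.10 but is not named in criterion 9; Tables 6–8 and the HCV list provide for baseline-positive patients whom the eligibility text excludes; and the viral monitoring in 6.2.10 is not carried into Appendix D. It matters for consistent enrolment and for the detection of reactivation. It should be corrected.

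Its size in patients is unknown. Testing is confined to patients with a listed risk factor, and the documents give neither the share who have one nor the prevalence of any marker. The conclusion for vaccine-derived antibody rests on a literal reading of 7.1, under which surface antibody counts as hepatitis serology because it is in the panel that 7.1 refers to. Nothing here changes the sample size or the primary analysis method. No view is taken on which clinical rule is right.

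**What to change.** The sponsor should reconcile criterion 9 (synopsis and Section 3.2), Section 6.2.10 with Tables 6–8, Sections 7.1 and 7.2, and Appendix D, so that:

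- one eligibility rule, worded the same wherever it appears, states which marker results exclude;
- that rule defines which tests count as hepatitis serology, says whether known or known active hepatitis is meant, and says how vaccine-derived surface antibody is treated;
- the management text agrees with that rule, including the actions set before the first dose and the handling of positivity first found on study;
- any viral monitoring the protocol requires appears in Appendix D and in the visit lists of Section 7.

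The content of the rule is the sponsor's clinical decision. The cost is a wording amendment with IRB review under Section 14.1. No change to sample size or SAP methods is needed.

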7.2 Baseline Study Assessments

The following information will be collected and procedures will be performed for each patient at screening:

- Informed consent form prior to performing any study related procedures
- Medical history
- Physical examination (PE), including measurements of height (baseline visit only), weight, and vital signs (resting heart rate, blood pressure, respiratory rate, oral temperature)
- ECOG PS (See Appendix A)
- Single ECG
- Concomitant medication review
- CBC including 3-part differential and platelets
- CMP to include: glucose, BUN, creatinine, sodium, potassium, chloride, calcium, CO2, alkaline phosphatase, AST, ALT, total bilirubin, total protein, and albumin (may be done up to 72 hours prior to treatment)

CONFIDENTIAL

STUDY DRUG(S): EVEROLIMUS
FINAL PROTOCOL DATE: 19 JUNE 2014

SCRI INNOVATIONS STUDY NUMBER: BRE 212
VERSION 1.0

- Fasting serum glucose
- Fasting cholesterol, HDL, LDL, and triglycerides
- HBV-DNA, HBsAg, HBc-Ab, and HBs-Ab serologic markers (applies only to patients with risk factors)
- HCV RNA testing (applies only to patients with risk factors)
- PT or INR, and PTT (if abnormal, repeat as clinically indicated)
- Serum pregnancy test for all pre/peri menopausal women (regardless of ovarian suppression)
- Urinalysis
- Blood sample for the VeriStrat® assay (See Appendix F)
- Block of archived tumor tissue if available (slides acceptable, see lab manual for details)
- CT scan of chest
- CT scan of abdomen and pelvis
- Bone scan (if abnormal, must be repeated at restaging)

7.3 Study Treatment Assessments

7.3.1 Cycles 1 and 2, Day 1

- Update of medical history
- PE including measurement of weight and vital signs
- ECOG PS (See Appendix A)
- AE assessment
- Concomitant medication review
- Study drug compliance assessment (Cycle 2, Day1)
- CBC, including 3-part differential and platelets
- CMP
- Fasting serum glucose
- Cholesterol, HDL, LDL, and triglycerides (Repeat only if abnormal at baseline)

7.3.2 Cycle 3, Day 1

- Update of medical history
- PE including measurement of weight and vital signs
- ECOG PS (See Appendix A)

CONFIDENTIAL

STUDY DRUG(S): EVEROLIMUS
FINAL PROTOCOL DATE: 19 JUNE 2014

SCRI INNOVATIONS STUDY NUMBER: BRE 212
VERSION 1.0

- AE assessment
- Concomitant medication review
- Study drug compliance assessment
- CBC, including 3-part differential and platelets
- CMP
- Fasting serum glucose
- Cholesterol, HDL, LDL, and triglycerides – every odd treatment cycle
- Serum or urine pregnancy test for all pre/peri menopausal women (regardless of ovarian suppression) every 2 cycles (8 weeks). If a urine pregnancy test is positive, it must be followed by a serum pregnancy test.
- CT scan of chest, abdomen and pelvis (See Section 7.4)
- Blood sample for the VeriStrat® assay (See Appendix F)

7.3.3 Cycle 4 +

- Update of medical history
- PE including measurement of weight and vital signs
- ECOG PS (See Appendix A)
- AE assessment
- Concomitant medication review
- Study drug compliance assessment
- CBC, including 3-part differential and platelets
- CMP
- Fasting serum glucose
- Cholesterol, HDL, LDL, and triglycerides-every odd treatment cycle (Repeat only if abnormal at baseline)
- Serum or urine pregnancy test for all pre/peri menopausal women (regardless of ovarian suppression) every 2 cycles (8 weeks). If a urine pregnancy test is positive, it must be followed by a serum pregnancy test.

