6.2.8 Management of Hyperlipidemia and Hyperglycemia

Treatment of hyperlipidemia should take into account the pre-treatment status and dietary habits of the patient. Blood test to monitor hyperlipidemia must be taken in the fasting state. Grade 2 hypercholesterolemia (>300 mg/dL or 7.75 mmol/L) or Grade 2 hypertriglyceridemia ($>2.5 \times$ ULN) should be treated with a 3-hydroxy-3-methyl-glutaryl (HMG)-CoA reductase inhibitor (e.g., atorvastatin, pravastatin) or appropriate lipid-lowering medication, in addition to diet.

Note: Concomitant therapy with fibrates and an HMG-CoA reductase inhibitor is associated with an increased risk of a rare but serious skeletal muscle toxicity manifested by rhabdomyolysis, markedly elevated creatine kinase (CPK) levels and myoglobinuria, acute renal failure and sometimes death. The risk versus benefit of using this therapy should be determined for individual patients based on their risk of cardiovascular complications of hyperlipidemia.

Dyslipidemia (including hypercholesterolemia and hypertriglyceridemia) has been reported in patients taking everolimus. Monitoring of blood cholesterol and triglycerides prior to the start of everolimus therapy and periodically thereafter as well as management with appropriate medical therapy is recommended.

Hyperglycemia has been reported in patients taking everolimus. Monitoring of fasting serum glucose is recommended prior to the start of everolimus and periodically thereafter. More frequent monitoring is recommended when everolimus is co-administered with other drugs that may induce hyperglycemia. Optimal glycemic control should be achieved before starting a patient on everolimus.

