Appendix D: Schedule of Assessments

Assessments	Baseline Study Assessments ^a	Study Treatment				Off-Treatment	Follow-Up	
		Cycles 1 and 2	Cycle 3	Cycle 4 +	Every 2 Cycles		Off Treatment Prior to Disease Progression ^l	Survival Follow-Up ^m
		Day 1	Day 1	Day 1		End of Study Treatment ^k		
Tests and Observations								
Informed consent	X							
Medical history	X	X	X	X		X	X	
Physical exam ^b	X	X	X	X		X	X	
ECOG PS	X	X	X	X		X	X	
ECG (single)	X							
Adverse event evaluation		X	X	X		X		
Concomitant medication review	X	X	X	X		X	X	
Study drug compliance assessment ^c		X	X	X		X		
Survival status								X
Laboratory Observations								
CBC, including 3-part differential, and platelets	X	X	X	X		X	X	
CMP ^d	X	X	X	X		X	X	
Fasting serum glucose	X	X	X	X		X		
Cholesterol/HDL/LDL/triglycerides ^{e,f}	X	X ^f	X	X ^f		X		
Hepatitis B and C screening	X ^o							
PT or INR, and PTT	X ^g							
Serum (or urine) pregnancy test ^h	X ^h		X ^h	X ^h		X ^h		
Urinalysis	X							
Archived tumor block	X ⁱ							
Serum sample for VeriStrat [®] assay	X ⁿ		X ⁿ			X ⁿ		X ⁿ
Staging								
CT scan of chest	X		X ^j		X ^j	X	X	
CT scan of abdomen and pelvis	X		X ^j		X ^j	X	X	
Bone scan	X ^j							

CONFIDENTIAL

SCRI INNOVATIONS STUDY NUMBER: BRE 212

VERSION 1.0

STUDY DRUG(S): EVEROLIMUS
FINAL PROTOCOL DATE: 19 JUNE 2014

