Appendix D: Schedule of Assessments (continued)

- a The physical examination including neurological examination, update of medical history, ECOG PS, CBC, CMP plus uric acid, magnesium, phosphorus, and PT or INR, PTT must be done \leq 7 days prior to initiation of treatment. However, if these initial examinations are obtained within 72 hours of Cycle 1 Day 1 they do not have to be repeated. Scans to document measurable or evaluable disease (i.e., tumor measurement) must be performed \leq 4 weeks prior to initiation of treatment.
- b Physical examination will include measurements of height (to calculate body surface area [BSA]), weight, and vital signs (resting heart rate, blood pressure, respiratory rate, oral temperature) at the Pre-Treatment Visit. Physical examinations (PE) done at all other times during the study will include only measurements of vital signs and weight.
- c Study drug compliance will be assessed at each patient visit. The study staff will count and document the amount of study drug taken and returned by the patient.
- d CMP will include measurements of glucose, BUN, creatinine, sodium, potassium, chloride, calcium, CO₂, alkaline phosphatase, AST, ALT, total bilirubin, total protein, and albumin.
- e Patients must fast at least 8 hours overnight prior to collection of the blood specimen.
- f Cholesterol/HDL/LDL/triglycerides do not need to be repeated on Cycle 1 Day 1 if they are normal at baseline. Repeat on Day 1 of every odd cycle.
- g If PT or INR, and PTT are normal at baseline they do not need to be repeated. Patients requiring the initiation of an anti-coagulation therapy during study treatment should have their coagulation test performed as clinically indicated.
- h A serum pregnancy test for all pre/peri menopausal women (regardless of ovarian suppression) is required at baseline \leq 7 days prior to date of first treatment. All pre/peri menopausal women will need a serum or urine pregnancy test every 2 cycles (8 weeks) before receiving study treatment. If a urine pregnancy test is positive, it must be followed by a serum pregnancy test.
- i Tumor specimens from the primary site or from metastatic lesions will be collected from all patients with available archived tissue. See lab manual for details.
- j Scans are required every 2 cycles, prior to the start of odd-numbered cycles beginning with Cycle 3. Bone scans that are abnormal at baseline must be repeated at restaging.

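### Protocol Section 7.3.3 and Appendix D disagree on lipid tests from Cycle 4; under 7.3.3 a patient with normal baseline lipids has no scheduled panel on drug after Cycle 3

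*Protocol*

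**What the plan says.** The protocol sets the lipid schedule in several places.

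- **Section 7.3.1 (Cycles 1 and 2):** "Cholesterol, HDL, LDL, and triglycerides (Repeat only if abnormal at baseline".
- **Section 7.3.2 (Cycle 3):** a panel for everyone, with the interval given as "every odd treatment cycle" and no baseline condition.
- **Section 7.3.3 (Cycle 4 and later):** "every odd treatment cycle (Repeat only if abnormal at baseline".
- **Section 7.5 (End of Study Treatment):** a panel for everyone. Appendix D footnote k puts this visit 30 days after treatment ends.
- **Appendix D, lipid row:** marked at baseline, Cycles 1 and 2, Cycle 3, Cycle 4+ and end of treatment. Footnote f is attached to the row and to the Cycles 1–2 and Cycle 4+ cells. It says the tests "do not need to be repeated on Cycle 1 Day 1 if they are normal at baseline", and then "Repeat on Day 1 of every odd cycle".
- **Section 6.2.8:** recommends "Monitoring of blood cholesterol and triglycerides prior to the start of everolimus therapy and periodically thereafter", without naming an interval or a baseline condition.

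Section 7.1 describes Appendix D as the complete schedule, but nothing states that it prevails over Section 7. The SAP does not address the lipid schedule.

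**The concern.** Sections 7.3.3 and Appendix D cannot both be followed for a patient whose lipids were normal at baseline. A site working from Section 7 in good faith would stop scheduled lipid testing after Cycle 3 Day 1 for as long as that patient stays on everolimus.

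The risk is a rise caused by the drug, so a normal baseline is no reason to stop looking. Section 6 lists hypercholesterolemia and hypertriglyceridemia among the most frequent laboratory abnormalities with everolimus. Section 6.2.8 says that Grade 2 values "should be treated with a 3-hydroxy-3-methyl-glutaryl (HMG)-CoA reductase inhibitor" or another suitable lipid-lowering drug, in addition to diet. That instruction works only if the values are measured. The metabolic profile done each cycle (components in Section 7.2) contains no lipids, so it does not fill the gap.

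There is also a reporting cost. Safety and tolerability form the secondary objective, and Section 10.4.3 summarizes laboratory results over the whole Safety Population. If the approximately 9 sites follow different rules, late lipid abnormalities will be detected unevenly.

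**Working it through.** The protocol states no figure to reproduce. The check sets the two rules side by side and counts panels.

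**Rules for a patient normal at baseline**

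| Visit | Section 7 | Appendix D, footnote f |
|---|---|---|
| Cycle 1 Day 1 | no panel | no panel (waived) |
| Cycle 2 | no panel | no panel (even cycle) |
| Cycle 3 | panel | panel |
| Cycles 5, 7, 9, … | no panel | panel |
| End of treatment | panel | panel |

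The texts part only from Cycle 5. For a patient abnormal at baseline they agree from Cycle 4 on.

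**Inputs**

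- Cycle length is 4 weeks (Section 5), so Cycle *k* Day 1 falls at week 4(*k* − 1): Cycle 3 at week 8, Cycle 5 at week 16, Cycle 7 at week 24.
- The end-of-treatment visit is 30 days after treatment (Appendix D footnote k): 30/7 = 4.29 weeks.
- One month = 30.4375/7 = 4.348 weeks.
- Illustrative treatment lengths are 2.8, 5 and 6.9 months, the median PFS values in Section 10.2.

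**Longest interval without a scheduled panel after Cycle 3**

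Each interval runs from the last on-treatment panel to the end-of-treatment visit.

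| Treated | Treatment ends | Visit | Under 7.3.3 | Under Appendix D | Panels lost |
|---|---|---|---|---|---|
| 2.8 months | week 12.2 | week 16.5 | 16.5 − 8 = 8.5 weeks | 16.5 − 8 = 8.5 weeks | 0 |
| 5 months | week 21.7 | week 26.0 | 26.0 − 8 = 18.0 weeks | 26.0 − 16 = 10.0 weeks | 1 (Cycle 5) |
| 6.9 months | week 30.0 | week 34.3 | 34.3 − 8 = 26.3 weeks | 34.3 − 24 = 10.3 weeks | 2 (Cycles 5, 7) |

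At 5 months, time on drug after the last scheduled panel is 21.7 − 8 = 13.7 weeks under 7.3.3, against 21.7 − 16 = 5.7 weeks under Appendix D. A patient treated 12 months (about 52 weeks) would lose five panels, at Cycles 5, 7, 9, 11 and 13.

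**How many reach Cycle 5 (illustration)**

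Assume time on treatment equals PFS and PFS is exponential. Cycle 5 starts at 16/4.348 = 3.68 months, and the share still treated is 2^(−3.68/median).

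| Median | Reach Cycle 5 | With a further 10% stopping earlier | With a further 20% |
|---|---|---|---|
| 2.8 months | 0.40 | 0.36 | 0.32 |
| 5 months | 0.60 | 0.54 | 0.48 |
| 6.9 months | 0.69 | 0.62 | 0.55 |

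The last two columns multiply by 0.9 and 0.8. They are there because patients also stop for toxicity or withdrawal, so the first column leans high. The 10% and 20% are assumptions. The shares apply to baseline-normal patients at sites that follow 7.3.3.

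**The case against.** The strongest counter-argument is that Appendix D, not Section 7.3.3, may be the misworded text. In the lipid row, the cell-level mark f sits on Cycles 1–2 and on Cycle 4+ but not on Cycle 3, which is where Section 7 does and does not place its baseline condition. The authors might have wanted conditional testing throughout and written footnote f too narrowly. The literal footnote explains the same pattern, however. The Cycles 1–2 cell needs the Cycle 1 waiver, the Cycle 4+ cell needs the odd-cycle rule because that column covers even cycles too, and Cycle 3 is always odd. Section 7.3.2 also states the odd-cycle rule without a condition. Intent cannot be proved from the text, so the sponsor should confirm it when making the change.

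Other points limit the harm:

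- Section 7.1 favors Appendix D, so a careful site may already be following it.
- Section 6.2.8 fixes no interval. It supports continued testing but cannot decide between the two schedules.
- Every patient still treated at Cycle 3 has a panel at week 8 under both texts, and an abnormal result there brings in 6.2.8. The realistic gap is in patients normal at both baseline and Cycle 3, a narrower group than the one counted above.
- Section 6 says most of the listed events have been Grade 1–2, and Table 4 exempts hypercholesterolemia from its Grade 3 interruption rule. A missed cholesterol value would therefore mainly delay medication. Table 4 does not name hypertriglyceridemia in that exemption.
- Tests on clinical grounds remain possible.

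These points reduce the consequence. They do not remove the contradiction.

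**Conclusion.** The concern holds. Section 7.3.3 and Appendix D footnote f give incompatible instructions for baseline-normal patients from Cycle 5 on, and a site that follows 7.3.3 does no scheduled lipid test on drug after week 8. The panel counts and intervals follow from the 4-week cycle and the 30-day visit once a treatment length is chosen. The share reaching Cycle 5 is an illustration that rests on exponential PFS standing in for time on treatment. The documents give neither the share normal at baseline nor the share of sites that would follow 7.3.3, so no count of affected patients is possible.

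The correction should be made because this is an operative monitoring rule for a common everolimus toxicity. The primary PFS analysis does not depend on it.

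**What to change.** In Section 7.3.3, delete the parenthesis that limits the lipid panel to patients abnormal at baseline, so that the bullet matches Appendix D footnote f.

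Leave Section 7.3.1 as it is. Cycle 2 is an even cycle, and footnote f asks for no panel then in baseline-normal patients. For patients abnormal at baseline, 7.3.1 asks for a Cycle 2 panel that footnote f does not list; that difference errs toward more testing and loses no monitoring.

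The cost is one parenthesis. No test is added beyond those Appendix D already requires.
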